3.14. END OF THE TRIAL

The trial will end with the last visit of the last patient recruited. Details of the planned chronogram can be seen in 3.21

As no interim analysis are planned (see 3.13), no formal stopping rules of the trial are considered in this regard.

The study may be terminated if the study procedures are not being performed according to Good Clinical Practice (GCP). The promotor also may terminate the entire study prematurely if concerns for safety arise within this study or in any other study with dapagliflozin.

3.15. ETHICAL ISSUES

At the recruitment visit, all patients meeting criteria and invited to participate will receive adequate written information on the study (Annex II) and will have the opportunity to ask the investigator any question regarding their participation and will be given enough time to make a decision. Following all this, they will sign and date their acceptance to participate in it (Annex III) prior to randomization. This is a trial

proposed as “low level of intervention trial” [“RD 1090/2015 de 4 de diciembre”] and every participant will be covered by an insurance for this instances.

This study will be done conforming to the principles of the Declaration of Helsinki and posterior amendments, Good Clinical Practice and the applicable legislation including the requirements of the Spanish law of data protection (“Reglamento General de Protección de Datos (Reglamento (UE) 2016/679 del Parlamento Europeo y del Consejo, de 27 de abril de 2016”, “Ley Orgánica 15/1999 de 13 de diciembre, de protección de datos de carácter personal”, and “RD1720/2007”), as described in the “Information for the patient sheet” (Annex II). Data will be entered online and stored securely in a centralized database in a devoted server. To access the eCRF, an user name and password with limited access to allow the development of the study will be assigned to every investigator in the trial (including coordinators and CRO). All personal identification data of the patients will be dissociated from the rest of the data and only the attending physicians will have access to that information to allow the follow-up. All data will be treated anonymously in the analysis and no report from the study will contain any information that allows to identify the patients.

The clinical study will be reviewed by health authorities and an ethic committee and the study will only be started when the approval from the regulatory authorities and the ethic committee is obtained.

At the end of follow-up, every patient will be informed of the treatment group in which he remained during the study and continue the standard care for his/her condition by his/her attending physician.

3.16. POTENTIAL RISKS AND BENEFITS OF THE STUDY

The drug under investigation is accepted and of common use in Spain for the treatment of the type of patients that will be included. It will be administered as approved in its specifications. Its use is evidence based and its safety and efficacy are well documented.

All tests and procedures included in the study are normal clinical practice in the diabetic patient with the exception of ABPM that poses no risk for the patient and is basic for the main outcome of the study.

3.17. QUALITY CONTROL

Filters and logic rules will be implemented in the electronic CRF to minimize data entry errors. Throughout the study, 10% of the clinical sites will be randomly selected and visited by CRO (ODDS, S.L.) staff to monitor quality of data.

3.18. SAFETY AND MONITORING OF ADVERSE REACTIONS

The Principal Investigator is responsible for ensuring that all staff involved in the study is familiar with the content of this section.

Adverse events will be monitored and registered during the study and communicated both to the promotor and to the “Agencia Española de Medicamentos y Productos Sanitarios” as by law (RD 1090/2015, December 4th).

3.18.1. Definition of adverse event

An adverse event (AE) is the development of an undesirable medical condition or the deterioration of a pre-existing medical condition following or during exposure to a

pharmaceutical product, whether or not considered causally related to the product. An undesirable medical condition can be symptoms (eg, nausea, chest pain), signs (eg, tachycardia, enlarged liver) or the abnormal results of an investigation (eg, laboratory findings, electrocardiogram). In clinical studies, an AE can include an undesirable medical condition occurring at any time, including run-in or washout periods, even if no study treatment has been administered.

The term AE is used to include both serious and non-serious AEs.

3.18.2. Definitions of serious adverse event

A serious adverse event (SAE) is an AE occurring during any study phase (i.e., screening, treatment, follow-up), at any dose of the study drugs that fulfils one or more of the following criteria:

- Results in death.
- Is immediately life-threatening.
- Requires in-patient hospitalization or prolongation of existing hospitalization.
- Results in persistent or significant disability or incapacity.
- Is a congenital abnormality or birth defect.
- Is an important medical event that may jeopardize the patient or may require medical intervention to prevent one of the outcomes listed above.

3.18.3. Definition of suspected unexpected serious adverse reaction (SUSAR)

As described in “REGULATION (EU) No 536/2014 OF THE EUROPEAN PARLIAMENT AND OF THE COUNCIL of 16 April 2014 on clinical trials on medicinal products for human use, and repealing Directive 2001/20/EC” the following definitions on suspected

unexpected serious adverse reaction (SUSAR) will apply in this protocol: A serious adverse reaction, the nature, severity or outcome of which is not consistent with the reference safety information.

The causality of SAEs (their relationship to all study treatment/procedures) will be assessed by the investigator(s) and communicated to the promotor/CRO.

3.18.4 Recording of adverse events

Time period for collection of adverse events

Adverse Events will be collected from time of signature of informed consent throughout the treatment period up to and including the 30-day follow-up period. All ongoing and any new AEs/SAEs identified during the 30 calendar days follow-up period after the last dose of study medication must be followed to resolution. After study treatment completion (i.e. after any scheduled post treatment follow-up period has ended) there is no obligation to actively report information on new AEs or SAEs occurring in study patients. If an Investigator learns of any SAEs, including death, at any time after a patient has completed 30 days post treatment follow-up period, and he/she considers there is a reasonable possibility that the event is causally related to the study treatment, the investigator should notify the promotor by reporting the SAE.

Follow-up of unresolved adverse events

Any SAE or non-serious adverse event that is still ongoing during the 30-day follow-up visit must be followed up to resolution unless the event is considered by the investigator to be unlikely to resolve, or the patient is lost to follow-up. AstraZeneca may request additional information for any patient with ongoing AE(s)/SAE(s) at the end of the study, if necessary.

The following variables will be collected for each AE:

- AE (verbatim).
- The date when the AE started and stopped.
- Whether the AE is serious or not.
- Investigator causality rating against the Investigational Product (yes or no).
- Action taken with regard to investigational product.
- Outcome.

In addition, the following variables will be collected for SAEs:

- Date AE met criteria for serious AE.
- Date Investigator became aware of serious AE.
- AE is serious due to.
- Date of hospitalization.
- Date of discharge.
- Probable cause of death.
- Date of death.
- Autopsy performed.
- Description of AE.
- Causality assessment in relation to Study procedure(s).
- Causality assessment in relation to Other medication.

It is important to distinguish between serious and severe AEs. Severity is a measure of intensity whereas seriousness is defined by the criteria in Section 3.18.2. An AE of severe intensity need not necessarily be considered serious. For example, nausea that persists for several hours may be considered severe nausea, but not a SAE. On the

other hand, a stroke that results in only a limited degree of disability may be considered a mild stroke but would be a SAE.

Adverse Events based on signs and symptoms

When collecting AEs, the recording of diagnoses is preferred (when possible) to recording a list of signs and symptoms. However, if a diagnosis is known and there are other signs or symptoms that are not generally part of the diagnosis, the diagnosis and each sign or symptom will be recorded separately.

Adverse Events based on examinations and tests

Deterioration as compared to baseline in protocol-mandated: laboratory values, vital signs should therefore only be reported as AEs if they fulfill any of the SAE criteria or are the reason for discontinuation of treatment with the investigational product.

If deterioration in a laboratory value/vital sign is associated with clinical signs and symptoms, the sign or symptom will be reported as an AE and the associated laboratory result/vital sign will be considered as additional information. Wherever possible the reporting investigator uses the clinical, rather than the laboratory term (eg, anemia versus low hemoglobin value). In the absence of clinical signs or symptoms, clinically relevant deteriorations in non-mandated parameters should be reported as AE(s s).

Deterioration of a laboratory value, which is unequivocally due to disease progression, should not be reported as an AE/SAE.

Any new or aggravated clinically relevant abnormal medical finding at a physical examination as compared with the baseline assessment will be reported as an AE.

Deaths

All deaths that occur during the study, or within the protocol-defined 30-day post-study follow-up period after the administration of the last dose of study treatment, must be reported

Reporting of serious adverse events

The investigator will report immediately (first 24 h) any SAE by means of filling and sending the corresponding form [Annex IX] to the CRO (ODDS, S.L.) by fax [[name]] or e-mail [[contact]].

The promotor/CRO must inform the AEMPS of any Suspected unexpected serious adverse events (SUSAR) that occur in accordance with the reporting obligations, and will concurrently forward all such reports to AZ. A copy of the report must be sent by e-mail to AstraZeneca at the time the event is reported to the AEMPS. It is the responsibility of the promotor to compile all necessary information and ensure that the AEMPS receives a report according to the AEMPS reporting requirement timelines and to ensure that these reports are also submitted to AstraZeneca at the same time.

* A **cover page** should accompany the **SAE** form indicating the following:

- External Scientific Research (ESR)
- The investigator's name and address
- The trial name/title and AstraZeneca ESR reference number

* Investigative site must also indicate, either in the SAE report or the cover page, the **causality** of events ***in relation to all study medications*** and if the SAE is ***related to disease progression***, as determined by the principal investigator.

* ***SAE report and accompanying cover pagewill be sentby way of Email to [contact].***

If a non-serious AE becomes serious, this and other relevant follow-up information must also be provided to AstraZeneca and the AEMPS.

Serious adverse events that do not require expedited reporting to the AEMPS need to be reported to AstraZeneca preferably using the MedDRA coding language for serious adverse events. This information should be reported under no circumstance less frequently than quarterly.

All SAEs have to be reported to AstraZeneca, whether or not considered causally related to the investigational product. All SAEs will be documented. The promotor is responsible for informing the Regulatory Authority of the SAE as per local requirements.

3.19. PUBLICATION POLICY

The investigators will submit the main results of the study to be published in a journal related to the topic of the trial.

3.20. CONDUCT OF THE STUDY

The table below shows the plan of visits for every patient participating in the study and

the procedures to be done at every visit and where it takes place.

	Visit 0 (recruitment&randomization)		Visit Week 4 (±3 days)	Visit Week 8 (±3 days)	Visit Week 12 (final visit)	Phone Call (30 days after the final visit)
	Primary care	Hospital (within 7 days from primary care visit)	Primary care	Primary care	Hospital	Hospital
Verification of inclusion and exclusion criteria and obtention of informed consent	✓					
Randomization and drug distribution for the entire follow-up		✓				
Personal and family history	✓					
Office BP	✓		✓	✓	✓	
Pill counting			✓	✓	✓	
Clinical exam	✓		✓	✓	✓	
Blood sample (to confirm entry criteria; recent [previous three months] analyses are acceptable) and urine	✓	✓ ^(*)			✓	
ABPM		✓			✓	
Adverse events monitoring			✓	✓	✓	✓

(*)

Only necessary if not all measurements in the blood sample drawn in primary are available

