3.2. PATIENTS

Type 2 diabetic patients recruited in the primary care setting in the area of three university hospitals in Madrid, irrespectively of the time since diagnosis and type of treatment received for their diabetes.

Entry criteria

- Patients with a previous diagnosis of type 2 diabetes and
 - Estimated glomerular filtration rate (eGFR) $\geq 60 \text{ mL/min} \times 1.73\text{m}^2$ and
 - Diagnosis of essential hypertension established at least one year before inclusion visit and suboptimal BP control (office BP above 140/70 mmHg)
 - HbA1C 7.5-10%
 - Albuminuria levels $\geq 30 \text{ mg/g}$ of creatinine

Exclusion criteria

- Age < 18 years old or ≥ 75 years old.
- Women of childbearing potential. A woman is considered of childbearing potential (WOCBP), i.e. fertile, following menarche and until becoming post-menopausal unless permanently sterile. Permanent sterilisation methods include hysterectomy, bilateral

salpingectomy and bilateral oophorectomy. A postmenopausal state is defined as no menses for 12 months without an alternative medical cause.

- Type 1 diabetes
- Albuminuria above 3000 mg/g of creatinine
- Established cardiovascular disease (stable heart failure, peripheral arterial disease or myocardial infarction or stroke within the previous 6 months)
- Intolerance to dapagliflozin
- On treatment with loop diuretic
- On treatment with SGLT2 inhibitors.
- On treatment with pioglitazone.
- Patients diagnosed of hereditary problems of galactose intolerance, Lapp lactase deficiency or glucose-galactose malabsorption.
- Patients who routinely work during nighttime (period between 11.00 p.m. and 7.00 a.m.)

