3.8. END POINTS

Primary: Changes in mean nocturnal BP from baseline (week 0) to last visit (week 12).

Secondary:

- Changes in office BP from baseline (week 0) to last visit (week 12).
- Changes in HbA1C from baseline (week 0) to last visit (week 12).
- Changes in albuminuria from baseline (week 0) to last visit (week 12).
- Natural variability of mean nocturnal BP on separate visits (placebo group).

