3.9. VISITS, VARIABLES AND MEASUREMENTS

Four clinical visits are planned in every patient at 0 (recruitment and randomization), 4, 8 and 12 weeks. Information on personal and family history of disease, clinical examination (including office BP determination), ABPM and blood and urine samples will be obtained on visits 0. The variables measured in the blood and urine samples depend on the criterium of the attending physician. For this trial, only HbA1c, serum creatinine, estimated glomerular filtration rate (eGFR) and albuminuria are mandatory. All this information, except personal and family history of disease, will also be collected at week 12 (see “3.20. Conduct of the study”). Thirty days after the end of the medication (visit of week 12) all participants will be contacted by telephone to assess safety. For the initial laboratory data required in the CRF, data obtained in primary care in the previous 3 months could be valid. These data will be repeated at the end of the study. Informed consents for the study will be signed by the patients before coming to the hospital. Blood samples extractions included in this protocol will be done, handled and analyzed at each clinical setting according to usual clinical

practice. No blood sample storage will be needed in this study. Extra blood samples drawn will be handled as described in “3.23. Addendum”.

The relationship of the procedures performed at every clinical visit is presented below (see “3.20. Conduct of the study”). Case report forms (CRFs) are presented in Annex I. Albuminuria will be measured according to generally used and previously described methodologies(18-23).

ABPM will be measured using Mobil-o-Graph that will give us 24 hours brachial and central BP as well as pulse wave velocity and heart rate(24). As diary of activity of the patient will not be recorded, in this study, nocturnal (or nighttime) blood pressure refers to measurements within the period from 12.00 p.m. to 6.00 a.m.

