3.12. DATA MANAGEMENT

Data will be collected in an electronic CRF by participating doctors and nurses both at the hypertension units and at primary care centers. A range of acceptable values and logical rules among variables will be implemented to improve quality of data and reduce the need of queries.

The processing, communication and transfer of data will be in accordance with the provisions of the Organic Law 15/1999, December 13th, on the protection of personal data.

Trial documentation will be kept and storaged in each site for 25 years after completion of the study.

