3.13. PLAN OF ANALYSIS

The main analysis will compare baseline and final visit values of nocturnal blood pressure and all the rest of quantitative variables of interest within each stratum of albuminuria by means of paired t-test. Changes of nighttime blood pressure from baseline to final visit among patients with high and very high albuminuria levels will be compared to placebo with t-test.

Variables will be described by means of mean (and standard deviation) or proportion depending on the type of variable considered. Whenever the test of hypothesis may involve discrete variables, chi-squared test will be used.

Comparability of treatment and placebo groups will be tested (t-student or chi-squared test, depending on the variable) to assess randomization, and linear regression will be used to adjust for potential confounders, if needed; stratum of albuminuria at randomization will be forced in the model.

To respond to secondary objectives, the same analyses will be done for each stratum of albuminuria at randomization.

Only patients that complete the 3-month follow-up will be analyzed. Patients who do not complete the follow-up will be compared to those who adhere to the protocol.

No interim analysis is planned. A *p* value<0.05 will be considered as statistically significant.

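### Baseline office BP is taken in primary care at the eligibility visit and the week-12 value in hospital, so the within-arm change in office BP includes any setting difference and regression to the mean

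*Combined protocol and SAP*

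**What the plan says.** Section 3.8 lists as a secondary endpoint "Changes in office BP from baseline (week 0) to last visit (week 12". Section 3.2 requires at entry "suboptimal BP control (office BP above 140/70 mmHg".

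The table in section 3.20 gives "the procedures to be done at every visit and where it takes place". Visit 0 is split into a primary-care part and a part headed "Hospital (within 7 days from primary care visit". Office BP is ticked in the primary-care part, in the same column as "Verification of inclusion and exclusion criteria and obtention of informed consent", and is blank in the hospital part. It is ticked again at weeks 4 and 8 (primary care) and at week 12 (hospital). ABPM is ticked in hospital both at visit 0 and at week 12.

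The text of section 3.9 agrees without naming a place: "clinical examination (including office BP determination), ABPM and blood and urine samples will be obtained on visits 0".

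Section 3.13 applies to nocturnal BP and "all the rest of quantitative variables of interest within each stratum of albuminuria by means of paired t-test" a comparison of baseline with final values. It writes out a t-test against placebo only for nighttime BP, then says that the secondary objectives get the same analyses by stratum.

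**The concern.** A change score is easiest to read when both readings are taken in the same way and the first was not used to select the patient. Here the two office readings come from different settings. The first also appears to be the one that had to exceed the threshold. A paired test cannot separate these influences from the drug. It could show a significant fall in office BP with no drug effect, or hide a real fall if hospital readings run higher.

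The plan avoids the change of setting for ABPM but not for office BP. Section 3.9 names the ABPM device, but no device or procedure is given for office BP that would align the two settings.

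**Working it through.** **The plan's own figures.** There is no sample-size or precision figure for office BP. The figures for nocturnal BP (section 3.11: difference 5 mmHg, SD 12, two-sided alpha 0.05, power 80%, 2:1 allocation, 9% drop-out) reproduce:

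- Placebo completers: (1.96 + 0.84)² × 12² × (1 + 1/2) / 5² = 68 after rounding up; active 136.
- Inflated for drop-out: 68/0.91 = 75 and 136/0.91 = 150, total 225.
- Per stratum (68 active, 34 placebo completers): (1.96 + 0.84) × 12 × sqrt(1/68 + 1/34) = 7.06, against the stated 7.1 mmHg.

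The present point changes none of these.

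**Regression to the mean.** Assumed inputs, none of them in the documents: office systolic BP normal with mean mu, SD 15, repeat correlation r, and selection on systolic BP above 140. The expected fall with no treatment and no change of setting is

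fall = (1 - r) × SD × phi(z) / (1 - Phi(z)), with z = (140 - mu)/SD.

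- mu = 135, r = 0.6: z = 0.333, phi/(1 - Phi) = 1.02, so 0.4 × 15 × 1.02 = 6.1 mmHg.
- mu = 145, r = 0.8: z = -0.333, phi/(1 - Phi) = 0.60, so 0.2 × 15 × 0.60 = 1.8 mmHg.

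| mu | r = 0.6 | r = 0.7 | r = 0.8 |
|---|---|---|---|
| 135 | 6.1 | 4.6 | 3.1 |
| 140 | 4.8 | 3.6 | 2.4 |
| 145 | 3.6 | 2.7 | 1.8 |

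With SD 12-18 and r 0.5-0.8 the range widens to 1.3-8.8 mmHg.

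**Effect on the two tests.** Simulation of one stratum (68 active and 34 placebo completers, mu 140, SD 15, no drug effect, 4,000 trials per row). Shift is an assumed hospital-minus-primary-care difference common to all patients.

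| r | Shift (mmHg) | Mean change, active | Paired test significant, active | Mean active - placebo | Between-arm test significant |
|---|---|---|---|---|---|
| 0.5 | -5 | -11.0 | 100% | 0.0 | 4.5% |
| 0.5 | 0 | -5.9 | 94% | 0.0 | 4.7% |
| 0.5 | +5 | -1.0 | 8% | 0.0 | 5.0% |
| 0.7 | -5 | -8.6 | 100% | 0.0 | 5.0% |
| 0.7 | 0 | -3.6 | 75% | 0.0 | 4.8% |
| 0.7 | +5 | +1.4 | 17% | 0.0 | 5.3% |
| 0.8 | -5 | -7.4 | 100% | 0.0 | 5.3% |
| 0.8 | 0 | -2.4 | 57% | 0.0 | 4.4% |
| 0.8 | +5 | +2.6 | 64% | 0.0 | 5.0% |

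With a true effect of -5 mmHg and r = 0.7, the between-arm estimate is -5.0 both with no shift and with a shift of +5. The within-arm change in the active group is -8.6 and -3.6 respectively.

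**Precision.** A shift common to all patients adds no variance to the between-arm contrast. If it varies between patients with SD s, the variance of change rises by the factor (sigma² + s²)/sigma². The documents give neither sigma nor s for office BP; the SD of 12 in section 3.11 is stated for nocturnal BP. No figure can therefore be put on the loss.

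**The case against.** The strongest reply is that this is a randomised, placebo-controlled trial with allocation stratified by hospital, so setting and selection act alike on both arms and cancel. That stands. A reader might infer from the visit table that the estimated drug effect on office BP is contaminated. The documents do not support this, and the simulated contrast is centred on zero under no effect with rejection close to 5%.

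Second, the distortion arises only if a before-after test is read as a drug effect, and regression to the mean would occur even if every reading were taken in one place. That also stands, and it is why the fix must cover the analysis as well as the measurement.

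Third, section 3.13 may intend the placebo comparison for office BP too, since office BP belongs to secondary objective 3 and the secondary objectives get the same analyses. This is a fair reading but not a secure one. The paired test is the only analysis plainly attached to office BP.

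Fourth, two links are inferred. No section says that the ticked baseline is the qualifying reading, although it is the only office BP listed at that visit. Nor does any section say that the observers differ: section 3.12 says only that data are collected "by participating doctors and nurses both at the hypertension units and at primary care centers".

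Finally, the weeks 4 and 8 readings in primary care allow a same-setting sensitivity check. They do not supply the week-12 endpoint, and a comparison with the qualifying baseline would still carry regression to the mean.

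**Conclusion.** The point holds for the within-arm change in office BP and no further. As written, the paired test includes any setting difference and regression to the mean. The latter is about 1.8-6.1 mmHg under the assumed mean of 135-145, SD of 15 and correlation of 0.6-0.8, and if the baseline is the qualifying reading. Section 3.11 cites falls of 4-8 mmHg in office BP with this drug class, so someone taking the within-arm change as a drug effect could be seriously misled. The setting component could go in either direction, and the documents give no figure for it.

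The dapagliflozin-placebo contrast is not biased by this; at most it loses an unquantified amount of precision. The sample size does not change, and neither does the primary endpoint. Staff know the allocation (section 3.5), which could bias office readings by arm; that is a separate matter which this point neither establishes nor resolves. Overall this is a cheap improvement to a secondary endpoint.

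**What to change.** Add office BP to the hospital part of visit 0, before the first dose, with the same device and procedure as at week 12. Use that reading as the office BP baseline and keep the primary-care reading for eligibility only. A second reading that is not used for selection matches the week-12 setting and largely removes regression to the mean.

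In section 3.13, state that office BP is assessed by comparing week-12 values between arms, adjusted for that baseline and albuminuria stratum, and that paired within-arm tests are descriptive only.

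The cost is one tick in the visit table, one CRF field and a few minutes at a visit patients already attend for ABPM and randomisation. The measurement has to be in place before enrolment, because a missing hospital baseline cannot be recovered later. The analysis statement costs nothing and is worth making even if the extra reading is not adopted.
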